Primary objectives	
To assess whether patients with bicuspid aortic valves that received a SAPIEN 3 / Ultra THV suffered from fewer complications
 
 • if valve size was identical to the one determined using the circle method 
compared to
 
 • a case where circle method derived valve size is different from the actually implanted valve
Secondary objectives	
To develop recommendations on how to size the valve using the circle method.

Exploratory research questions / endpoints	
We aim to assess whether patients with bicuspid aortic valves that received a SAPIEN 3 / Ultra THV suffered from fewer complications
 
 • if valve size was identical to the one determined using the circle method 
compared to
 
 • a situation where circle method derived valve size is different from the actually implanted valve 
Complications are defined as:
 
 • Death • Stroke • Paravalvular Leakage (PVL) • Pacemaker implantations • Coronary occlusion • Malposition • Fistula to right ventricular outflow tract (RVOT) • Annulus rupture • Sinus sequestration • Valve embolisation
Schedule	
Baseline, Intervention, Discharge, 30 days, 3 months/12 months (according to availability, all retrospective)

Quality assurance / CoreLab	A CoreLab with the 3mensio Software and the most recent update as of January 2021 will be available to assess the CT data matching each patient. The two CoreLab physicians will independently assess the CT data based on the manual provided in the appendix. These data will be collated with the clinical dataset to assess correlations between measurements and complications / outcomes.
Statistics	No pre-specified statistical analyses, explorative approach.
Sample size	Given the limited data for sizing and positioning with the circle method in BAV patients, we aim to include at least 60 patients for this pilot study.

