2.1 CLINICAL BACKGROUND

The bicuspid aortic valve (BAV) is the most common heart valve abnormality, affecting 0.4% to 2.25% of the general population and up to 6% of patients with severe aortic stenosis (AS) (2). Although BAVs do not usually pose any risks at birth and during early life, they are associated with a number of cardiac complications during the adulthood, including AS, infective endocarditis, aortic dilatation, and aortic dissection (3). Progressive regional calcification is also common in BAVs and is identical to that occurring in tricuspid aortic valves (TAV).

Transcatheter aortic valve replacement (TAVI) has become a standard treatment option for patients with severe AS who are considered high risk for surgical aortic valve replacement (4-6). The presence of BAV has been considered a contraindication to TAVI due to BAV's anatomical features (large annulus, calcified raphe, aortic root dilatation, and horizontal aorta) that may adversely impact procedural outcomes (7). Consequently, patients with BAV have constantly been excluded from the major randomized trials involving TAVI, despite promising results from a series of registries and observational reports (8-11). However, in light of the evidence from recent trials indicating TAVI to be a safe alternative to surgery for low risk patients, more patients with BAV are now being considered for TAVI (12-15).

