Due to the existing knowledge gap on TAVI in BAV patients, several issues, including sizing and positioning of the device, remain unresolved. Currently, sizing in BAV includes three different techniques: an annular sizing, a supra-annular sizing, or a balloon sizing. Several trials proposed various BAV classifications in order to define anatomical differences, predict complications, and identify orifice area/patient aortic annulus area ratio. The most commonly used BAV classification was established by Sievers and Schmidtke, who used the number of raphe to distinguish three major anatomical types: type 0 (no raphe), type 1 (one raphe), and type 2 (two raphe), followed by two additional characteristics, including spatial position of raphe and functional status of the valve (16). Recently, the Bicuspid Aortic Valve Anatomy and Relationship with Devices (BAVARD) program used the annular-based sizing and intercommissural distance (ICD) to predict sealing, position, and size of the device, potentially avoiding excessive oversizing and its consequences (17). The objective of this program was to identify the sizing ratios used for TAVI in BAV, assess the prostheses' geometry after implantation and compare the results with the TAV patients. Tchetché et al. retrospectively analyzed 101 patients with BAV with available pre- and post-TAVI multidetector computed tomography and compared them with 88 TAV patients (17). The authors concluded that annular-based sizing in BAV was valid in selecting the TAVI device size while supra-annular sizing could be used in cases when the mean annular diameter is larger than the ICD (17). In addition, Petronio et al. proposed another novel approach called Calcium Algorithm Sizing for bicuspid Evaluation with Raphe (CASPER) (18). The algorithm focuses on the combination of three major anatomical features: raphe length with respect to annulus diameter, calcium burden, and calcium localization in relation to raphe. However, this method was validated in a relatively small patient cohort and further trials with larger population of patients with BAV and different morphological varieties are needed.

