Annular sizing remains the major treatment approach in most patients with BAV, yet some BAV anatomies may require sizing at the supra-annular level. Because of the unequal-sized leaflets and reduced number of commissures, the orifice in BAV is usually smaller, more asymmetrical, and less circular than in TAV. As a result, the leaflets do not open in the same way during TAVI and conventional

annular sizing may result in over-sizing at the level of the leaflets, leading to more asymmetry and increased risk of trauma related to calcification in the aortic valvular complex (1).

Blackman et al. recently published guidelines for sizing and positioning the balloon-expandable Edwards SAPIEN 3/Ultra transcatheter heart valve (THV) in BAV (1). The consensus describes the following anatomical factors that influence sizing optimization in patients with BAV:

- 1) *Calcification of the raphe*. Severe raphe calcification reduces valve expansion or may cause malpositioning of the transcatheter heart valve (THV), leading to potential undersizing relative to the aortic annulus
- 2) *Calcification of the cusps*. In case of an extreme calcification of the cusps, relative undersizing should be considered as anchoring in the supra-annular space is enhanced.
- 3) *Configuration of the aortic valve*. Relative undersizing may also be considered in patients with a tapered, as opposed to tubular or flared, valve configuration, i.e., where the supra-annular space is smaller.
- 4) *Large annuli*. A large annular area (above the upper limit of the SAPIEN 3 sizing chart) is often the case in patients with BAV and sizing to the supra-annular space should be considered.

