4 PARTICIPATING SITES

4.1 PARTICIPATING SITES

The project aims to collect data in three medical centers in Germany, Poland and the United Kingdom. A mean of 20 patients will be enrolled per site during a period of 6 months.

Site selection is based on the site's prior experience and patient availability.

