8.2 DESCRIPTIVE ANALYSIS

Statistical analysis will be performed for the total study population. Continuous variables will be presented as mean \pm SD or as median with interquartile range, and categorical variables (e.g. gender) will be reported as frequencies and percentages. The Kolmogorov-Smirnov test will be used to test for normal distribution. For comparisons, Chi-Square or Fisher exact test will be used for categorical variables, and Student's t-test or Mann-Whitney U for continuous variables.

All statistical analyses will be performed using IBM SPSS Statistics version 29 (IBM, Armonk, New York) or R Core Team (<https://www.R-project.org/>).

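### Section 8.2 lists only unadjusted tests for a non-randomised primary contrast; if anatomy affects whether implanted and circle-derived sizes agree, the crude result is confounded, so one pre-named adjusted estimate should sit beside it

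*Combined protocol and SAP*

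**What the plan says.** Sections 1 and 3.2.1 set the primary objective: to validate the circle method, in particular by asking whether complications were fewer when the implanted size matched the circle-derived size than when it did not. Section 3.1 describes the project as retrospective and non-interventional.

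Section 8.2 is the only place with analysis methods. It gives descriptive summaries, a normality test and two-variable tests on the total population: "For comparisons, Chi-Square or Fisher exact test will be used for categorical variables", and the t-test or Mann-Whitney U for continuous variables. It does not assign any test to the primary contrast. It names no regression, stratification, matching or covariate. The synopsis adds "No pre-specified statistical analyses, explorative approach" and, for the core-lab CT data, "These data will be collated with the clinical dataset to assess correlations between measurements and complications / outcomes", without a method.

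Section 2.1 ties anatomy to both sides of the question:
- On sizing: "The consensus describes the following anatomical factors that influence sizing optimization in patients with BAV", followed by raphe calcification, cusp calcification, valve configuration and large annuli.
- On outcome: bicuspid valves have "anatomical features (large annulus, calcified raphe, aortic root dilatation, and horizontal aorta) that may adversely impact procedural outcomes".
- On both at once: "Severe raphe calcification reduces valve expansion or may cause malpositioning of the transcatheter heart valve (THV), leading to potential undersizing". Malposition is itself one of the listed complications.

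**The concern.** In a non-randomised comparison, a factor that predicts both group membership and outcome produces a crude difference even when the exposure does nothing. The protocol's own background names two candidates, raphe calcification and large annulus, and the listed tests can account for neither. A crude difference in complications, or its absence, could then partly reflect which valves were hard to treat and not whether the circle method picked the better size.

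The result is meant to support a validation claim, and the secondary objective is to develop sizing recommendations. A misleading crude contrast could feed into both. Since nothing is pre-specified, any adjustment made later could be chosen after the results are known.

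**Working it through.** **The plan's own figure.** Three sites at an average of 20 patients give 3 × 20 = 60, which agrees with section 8.1. The documents give no event rate, group split, alpha or power, so the bias cannot be derived from them. (Sections 3.1 and 4.3 speak of 40 patients; that needs separate reconciliation, and 60 is used here.)

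**The three links that confounding needs.**
1. Anatomy to outcome: stated in section 2.1.
2. Anatomy to size choice: stated in section 2.1.
3. Anatomy to agreement between implanted and circle-derived size: not stated. Section 2.1 says there are no strict sizing thresholds, which makes disagreement in difficult anatomy plausible. It also says the circle is matched to the patient's anatomy, so both sizes could move together.

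**Illustration; every input is assumed.** Binary independent factors, each with prevalence 0.4; d = probability of being in the *different* group; r = complication risk; no true effect of agreement.

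One factor, d = 0.60 with it and 0.30 without, r = 0.40 and 0.15:
- P(different) = 0.4 × 0.60 + 0.6 × 0.30 = 0.42.
- Factor prevalence: 0.24 / 0.42 = 0.571 in *different*; 0.16 / 0.58 = 0.276 in *identical*.
- Crude risks: 0.15 + 0.25 × 0.571 = 29.3%; 0.15 + 0.25 × 0.276 = 21.9%. Spurious difference: 7.4 points.

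Two factors, d = 0.20 + 0.25 for each present, r = 0.10 + 0.20 for each present:
- P(different) = 0.20 + 0.25 × 0.8 = 0.40.
- Prevalence of each factor: 0.4 × 0.55 / 0.40 = 0.55 in *different*; 0.4 × 0.45 / 0.60 = 0.30 in *identical*.
- Crude risks: 0.10 + 0.40 × 0.55 = 32.0%; 0.10 + 0.40 × 0.30 = 22.0%. Spurious difference: 10.0 points.

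Simulated means (SD) in percentage points, *different* minus *identical*, n = 60, 20,000 runs:

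| Assumed case | Crude | Mantel-Haenszel on one factor | Firth on two factors |
|---|---|---|---|
| One factor | 7.4 (11.5) | 0.0 (11.8) | – |
| Two factors | 10.0 (11.8) | 5.3 (12.2) | 0.4 (11.3) |
| Two factors, read with 80% sensitivity and specificity | 10.1 | 8.5 | 6.7 |
| Third factor unmeasured (d 0.10 + 0.25 each, r 0.08 + 0.15 each) | 11.4 (11.9) | 8.1 (12.4) | 4.5 (11.8) |
| Mild (d 0.25 + 0.15 each, r 0.10 + 0.10 each) | 3.1 (10.6) | 1.6 (10.7) | 0.5 (10.2) |
| No link to agreement (d 0.40) | -0.1 | -0.1 | 0.2 |
| Reversed (d 0.60 - 0.25 each) | -10.0 (11.3) | -5.4 (11.6) | 0.0 (11.8) |
| Opposing (d 0.40 + 0.25 and - 0.25) | -0.1 (11.7) | -5.4 (11.7) | 0.3 (11.6) |

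The exact three-factor difference is 32.75% - 21.5% = 11.25 points; 11.4 is the simulated mean.

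**Precision.** 1.96 × 10.2 = 20.0 and 1.96 × 12.4 = 24.3, so a 95% interval is about ±20 to 25 points whichever estimate is used.

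**Room for adjustment.** Agreement plus two covariates is three parameters. At 5 events per parameter this needs 15 events; at 10 it needs 30. Expected events are 60 × 0.26 = 15.6 in the two-factor case and 60 × 0.18 = 10.8 in the mild case. Fewer than 10 events occurred in 3% and 34% of runs respectively. A penalised model with two covariates is therefore about the limit.

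**Stratifying on one factor.** In the opposing case, stratifying on one factor moves a crude result near zero to -5.4. A fallback that stratifies on raphe calcification alone could therefore do harm.

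**The case against.** The strongest objection is that the third link is missing from the documents. If the circle follows the same anatomy as the operator's choice, agreement may be unrelated to anatomy and the crude contrast is unbiased by it; the no-link row shows this. A reader might infer that the protocol documents the confounding, or that the bias favours the circle method. Neither is supported. Nor is it right to read section 8.2 as assigning an unadjusted test to the primary contrast, because it assigns none; the point is that nothing else is listed.

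The benefit of adjusting may also be modest. In the mild case, root mean squared error falls only from 11.0 to 10.2 points. A Firth model with no covariates already reaches 10.7, so part of that gain comes from the penalty. Fisher's test rejected in 4.6% of mild null runs, which is not inflated, and in 10.9% in the strong two-factor case. Misread or unmeasured anatomy leaves much of the bias in place. These points stand, and they argue for a small fix.

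Finally, the project is labelled an exploratory pilot and section 8.2 is headed as descriptive. That lowers the severity. It does not remove confounding, and the objective is still worded as validation. The planned correlations show an intention to relate CT findings to outcome, but without a method they are not an adjusted analysis.

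Differences between sites could confound as well, but no passage suggests that the three centres differ in agreement or risk. A site-stratified analysis is therefore optional.

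**Conclusion.** The point holds in conditional form. The primary contrast is observational, only unadjusted tests are listed, and the protocol itself links raphe calcification and large annulus to sizing and to outcome. If these features also affect agreement, the crude difference is confounded.

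Direction and size cannot be taken from the documents. The assumed cases run from -10 points through 0 to about +11, and they rest on invented prevalences, risks and links. At 60 patients the interval is wide either way, so adjustment cannot turn this into a validation study. A reader might infer that an adjusted result would establish the method; the misread-anatomy and unmeasured-factor rows show why it would not.

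This is an inexpensive improvement worth making. It does not show that the planned result would be wrong.

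**What to change.** In section 8.2, set before the groups are compared:

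1. Tabulate by agreement group the anatomy that section 2.1 names (raphe calcification, cusp calcification, valve configuration, annulus area) and site.
2. For an any-complication outcome built from the listed complications, at 30 days, report the crude risk difference (*different* minus *identical*) with 95% CI. Beside it, report one pre-named Firth logistic estimate with agreement, raphe calcification and annulus area, standardised to a risk difference with a bootstrap 95% CI. First confirm that the core lab records both covariates; the measurement manual is not in the text supplied. State in advance the raphe categories, including where valves without a raphe go, and how annulus area enters the model, since the illustration tested only binary factors.
3. With fewer than 10 events, report the crude result and the anatomy table only. Do not fall back on stratifying by raphe calcification alone.
4. Word the conclusion as an association subject to residual confounding, not as validation of the circle method.

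Cusp calcification and valve configuration stay in the table and out of the model because the expected events do not support more terms; the SAP should say so.

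The cost is a few lines of SAP text, one table and one model on CT data that the synopsis already plans to join to the clinical dataset. The interval may be slightly wider, and control of confounding will remain incomplete.

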9 ETHICAL AND REGULATORY CONSIDERATIONS

9.1 DECLARATION OF HELSINKI

The project will be conducted in accordance with the recommendations guiding physicians in biomedical research involving human subjects adopted by the 18th World Medical Assembly, Helsinki, Finland, 1964 and later versions. Specific country regulations will be complied with.

9.2 GOOD CLINICAL PRACTICE

The project will be conducted in accordance with the European Medical Device Regulation (Regulation (EU) 2017/745 of 5 April 2017) and ISO 14155:2011.

9.3 PATIENT INFORMED CONSENT

It is the responsibility of the investigator to provide each patient with full and adequate verbal and written information regarding the objectives of the project before inclusion in the project. Besides, the patient will be informed that there are no potential risks (due to the non-interventional, retrospective character of the project) and no guaranteed benefits as a result of participation in this project. The participation in the project is completely voluntary and the patient will not be paid to take part in the registry. The CRO will provide the patient information and informed consent template / data protection statement for the registry. The patient consent will be given by signing the patient informed consent form.

It is the responsibility of the investigator to obtain a signed informed consent from all patients enrolled in the registry. The retrospective patients will give their written approval prior to the data entry into the eCRF system (unless otherwise agreed by the local IRB/IEC). If the patient refuses to sign the informed consent, patient data will not be collected.

Consent may be withdrawn by the patient at any time, without giving reasons and without leading to disadvantages with regard to further medical care. If the patient withdraws from the registry, any (data) material already obtained will be destroyed.

9.4 INSTITUTIONAL REVIEW BOARD/INDEPENDENT ETHICS COMMITTEE (IRB/IEC)

Each site is responsible for adhering to the rules and regulations of its institution, ethics committee, and local and national authorities regarding releasing patient data.

IPPMed will provide the protocol (in English) to the investigators who should get in touch with their local ethics committee and seek approval. Ethics approval has to be obtained by the time of first patient inclusion. If ethical approval is denied, sites will not be able to participate in the project.

9.5 DATA PROTECTION AND PATIENT CONFIDENTIALITY

IPPMed is dedicated to maintaining the confidentiality and privacy of patients whose data are enrolled in the project. Passwords are issued to appropriate personnel to ensure confidentiality and protection of the database by allowing variable levels of access to the computer system. All project documents will only identify the patient by a patient project identification number assigned by the CRO.

9.6 PUBLICATION POLICY

In case of a publication, authors will base their authorship on the published ICMJE criteria (19). The order of authors will be determined based on their role, their contribution to the manuscript development and their patient numbers contributed to the project.

Clinical sites have the right, consistent with academic standards, to publish their individual results independent from this project. The site agrees to share any proposed submission for publication with the CRO prior to submission.

10 FUNDER AND CONFLICT OF INTEREST INFORMATION

The registry is funded by an investigator initiated grant from Edwards Lifesciences ([name]). The funding body will not contribute to the collection, analysis or interpretation of the collected data. IPPMed has received research funding, and honoraria for consultancy from Edwards Lifesciences. Some of the investigators have received proctoring fees from Edwards Lifesciences and other medical devices manufacturers in the the past.

10.1 GENERAL LIABILITY

The project device is commercially available and has insurance coverage for the country specific requirements for commercial device liability.

